6.7. Safety endpoint (SS)

6.7.1. Symptomatic intracranial hemorrhage within 24 hours postoperatively

Table33 Symptomatic intracranial hemorrhage within 24 hours postoperatively

Item	Indicator	Experimental Group	Control Group	Total
Symptomatic intracranial hemorrhage within 24 hours postoperatively	No n(%)			
	Yes n(%)			
	Total (Missing)			
	Statistical measure			
	P-value			

Note: Symptomatic intracranial hemorrhage within 24 hours postoperatively refers to intracranial hemorrhage detected on cranial CT or MR imaging during the 24-hour postoperative follow-up, accompanied by an increase in NIHSS score of ≥ 4 points compared to the preoperative score.

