Evaluation method: The recanalization time will be judged by intraoperative procedure and the vascular condition shown by imaging.

Formula: Recanalization time = Recanalization success time - Femoral artery puncture time

Precautions: The recanalization time is the time from the completion of femoral

artery puncture to recanalization success. If the vessel is not revascularized, the end time point is recorded as the time point at the end of operation. Criterion for instant recanalization success: target vessel recanalization with mTICI grade of 2b or 3 after thrombectomy with the investigational device. The investigator's judgment intraoperatively shall prevail.

- **Proportion of subjects with NIHSS score decrease > 4**

Recording time and method: The preoperative and postoperative NIHSS scores are compared by three time points: pre-operation, 24 ± 12 h postoperatively and 7 ± 2 d postoperatively (before discharge in case of premature discharge) to analyze the degree of impairment and improvement of neurological functions preoperatively and postoperatively. The NIHSS score is the total score based on NIHSS scale (as shown in Appendix 5).

Proportion of subjects with NIHSS score decrease > 4 = Number of subjects with NIHSS score decrease > 4 postoperatively in this group/Number of subjects treated with thrombectomy through stents in this group $\times 100\%$.

- **Success rate of device operation**

Definition: The success rate of device operation is the proportion of device operation success. Device operation success is defined as successful delivery of the investigational device to the diseased vessel site to complete accurate deployment and withdrawal.

Evaluation time: Intraoperatively (evaluation endpoint)

Evaluation site: target vessel

Evaluation method: The success rate of device operation is calculated by intraoperative evaluation of whether the delivery, deployment and withdrawal of the thrombectomy device are completed.

Formula: Device operation success = Number of devices delivered, deployed and withdrawn/Number of all investigational devices used in this group $\times 100\%$.

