6.1.7. Safety Evaluation Methods

6.1.7.1. Description of Safety Endpoints

1) Safety Endpoints

- Safety endpoints: Incidence of symptomatic intracranial hemorrhage within 24 h postoperatively, mortality within 90d, incidence of SAE, incidence of AE, and incidence of device defects.
- #### **2) Selection of Method and Time to Evaluate, Record and Analyze the Safety Endpoints**
- **Incidence of symptomatic intracranial hemorrhage within 24h**

Recording time and method: Symptomatic intracranial hemorrhage within 24h, specifically refers to intracranial hemorrhage (parenchymal hematoma, subarachnoid hemorrhage, ventricular hemorrhage) accompanied by neurological deterioration (NIHSS score increases by ≥ 4 compared with that preoperatively).

Incidence of symptomatic intracranial hemorrhage within 24 h = Number of subjects who develop symptomatic intracranial hemorrhage on CT or MR within 24 h in this group/Number of subjects who receive revascularization device for thrombectomy in this group $\times 100\%$.

* Subjects with symptomatic intracranial hemorrhage postoperatively who show additional hemorrhage on CT or MR within 24 h postoperatively will not be re-evaluated.

● All-cause mortality within 90 days

Recording time and method: Throughout the clinical trial. All-cause mortality = Number of deaths in this group/Number of subjects who receive revascularization device for proximal thrombectomy in this group $\times 100\%$.

● Incidence of device defects

Recording time and method: During the thrombectomy. Incidence of device defects = Number of defective devices / Total number of devices $\times 100\%$.

Note: The investigational device defects that occur during the clinical trial, such as device fracture and mislabeling.

● Incidence of SAE

Recording time and method: Throughout the clinical trial. Incidence of SAE = Number of subjects with SAE/Number of subjects treated with intracranial thrombectomy device for thrombectomy in total $\times 100\%$.

● Incidence of AE

Recording time and method: Throughout the clinical trial, incidence of AE = Number of subjects with AE/Number of subjects who receive intracranial thrombectomy device for thrombectomy $\times 100\%$.

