13.3. SAE

The SAE refers to the event that causes death or serious deterioration of health in the process of clinical trial, including:

- Fatal disease or injury;
- Permanent impairment of a body structure or a body function;
- Requiring in-patient hospitalization or prolongation of existing hospitalization;
- Requiring medical treatment or surgical intervention so as to avoid permanent impairment of the body structure or body function;
- Leading to a fetal distress, fetal death or a congenital abnormality;
- Congenital defect, etc.

Hospitalization or prolongation of hospitalization cannot be considered an SAE if at least one of the following exceptions is met:

- 1) Pre-planned hospitalizations (e.g., scheduled elective or scheduled operations or examinations prior to study start)
- 2) Hospitalization not related to an AE (e.g., community hospitalization for short-term or long-term care purposes)
- 3) Measures such as tracheal intubation or tracheotomy to help stroke patients breathe better with sputum
- 4) Not symptomatic intracranial hemorrhage as judged by the investigators

Note: Symptomatic intracranial hemorrhage refers to intracranial hemorrhage (parenchymal hematoma, subarachnoid hemorrhage, ventricular hemorrhage) accompanied by neurological deterioration (NIHSS score increases by ≥ 4 compared with that preoperatively)

However, any interventional therapy performed during hospitalization may meet the criteria for a "significant medical event" and may be reported as a SAE based on clinical judgment. In addition, if local regulatory authorities specifically require stricter definitions, local regulations shall prevail.

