2.2. Safety Endpoints

1. Incidence of symptomatic intracranial hemorrhage within 24 hours postoperatively: Symptomatic intracranial hemorrhage refers to intracranial hemorrhage (cerebral parenchymal hematoma, subarachnoid hemorrhage, subdural hematoma, ventricular hemorrhage) accompanied by neurological deterioration (NIHSS score increase ≥ 4 points compared to preoperative). Incidence of symptomatic intracranial hemorrhage within 24 hours = Number of subjects in this group with symptomatic intracranial hemorrhage confirmed by CT or MR within 24 hours / Number of subjects in this group undergoing intracranial thrombectomy with a thrombectomy stent $\times 100\%$. CT or MR findings were evaluated by the central reading center.
2. All-cause mortality within 90 days postoperatively: All-cause mortality rate = Number of deaths in this group / Total number of subjects in this group undergoing intracranial thrombectomy with a thrombectomy stent $\times 100\%$.
3. Incidence of SAEs, incidence of AEs.
4. Device defects rate.

3. Analysis Set

Full Analysis Set (FAS): A population defined according to the intention-to-treat principle, comprising all subjects who participated in randomization and received the study product. For patients in whom the primary efficacy endpoint was not observed, missing data will be carried forward using

the Worst Observation Carry Forward (WOCF) strategy.

Protocol-Compliant Set (PPS): Refers to the subgroup of the treated population that completed the trial, excluding those with major protocol deviations (e.g., subjects violating inclusion or exclusion criteria).

Safety Set (SS): Refers to the population of all subjects who used the study device and had at least one safety assessment.

Efficacy analyses will be conducted on the basis of the full analysis set and the per-protocol set. Additionally, all baseline demographic analyses will be performed on the full analysis set, while safety evaluations will be conducted on the safety set.

4. Missing Data Imputation

For patients in the FAS who did not have an observed primary efficacy endpoint, worst-case imputation was applied, defined as failure to achieve immediate reperfusion in the target vessel. No imputation was performed for secondary endpoints or efficacy data in the PPS. Missing safety data were not imputed.

5. Statistical Analysis Methods

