6.7.3. Adverse Events

Table35 Summary of Adverse Events

Item	Experimental Group (n=)		Control Group (n=)		Total (n=)	
	Number of Occurrence	Incidence Rate (%)	Number of Occurrence	Incidence Rate (%)	Number of Occurrence	Incidence Rate (%)
Adverse Event						
Mild adverse events						
Moderate adverse events						
Severe adverse events						
Adverse events related to the investigational device						
Adverse events leading to subject withdrawal from the trial						
Adverse events resulting in death						

Note: Definition of trial device-related adverse events: Adverse events classified as "definitely related," "probably related," "possibly related," or "unclassifiable" to the trial device.

Table36 Summary of Serious Adverse Events

Item	Treatment Group (n=)			Control group (n=)			Total (n=)		
	Occurrence	Number of Subjects	Incidence Rate (%)	Occurrence	Number of Cases	Incidence Rate (%)	Number of cases	Incidence Rate (%)	P value
Serious Adverse Events related to the investigational device									
Serious adverse events resulting in death									

Note: Definition of serious adverse events related to the investigational device: Serious adverse events determined to be "definitely related," "probably related," "possibly related," or "unclassifiable" to the investigational device.

Table37 Event Coding

Item	Experimental Group (n=)			Control Group (n=)			Total (n=)		
	Occurrence	Number of Subjects	Incidence Rate (%)	Occurrence	Number of Cases	Incidence Rate (%)	Number of cases	Incidence Rate (%)	P value
Adverse Event									
SOC1									
PT1									
PT2									
.....									
SOC2									
.....									

Table38 Serious Adverse Event Codes

Item	Experimental Group (n=)			Control Group (n=)			Total (n=)		
	Occurrence	Number of Subjects	Incidence Rate (%)	Occurrence	Number of Cases	Incidence Rate (%)	Number of cases	Incidence Rate (%)	P value
Serious Adverse Events									
SOC1									
PT1									
PT2									

	Experimental Group (n=)	Control Group (n=)	Total (n=)	
Item	Number of Occurrence Subjects	Incidence Rate (%)	Number of Cases	Incidence Rate (%)
.....				
SOC2				
.....				

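### The sICH definition has no death alternative to the NIHSS rise, so a treated patient with an imaged bleed who dies unscored cannot count as sICH

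*SAP*

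**What the plan says.** Four places define sICH, and all four describe deterioration only as an NIHSS rise of at least 4 over the preoperative score.

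- Protocol 6.1.7.1 gives that rule, and its 24 h numerator also requires imaging: "Number of subjects who develop symptomatic intracranial hemorrhage on CT or MR within 24 h in this group".
- The note in protocol 13.3 repeats it: "Symptomatic intracranial hemorrhage refers to intracranial hemorrhage (parenchymal hematoma, subarachnoid hemorrhage, ventricular hemorrhage) accompanied by neurological deterioration", followed by the same NIHSS threshold.
- SAP 2.2 item 1 lists "subarachnoid hemorrhage, subdural hematoma, ventricular hemorrhage) accompanied by neurological deterioration", again with the NIHSS threshold, and requires CT or MR confirmation within 24 hours. The denominator is "Number of subjects in this group undergoing intracranial thrombectomy with a thrombectomy stent".
- The SAP Table 33 note counts a bleed "detected on cranial CT or MR imaging during the 24-hour postoperative follow-up, accompanied by an increase in NIHSS score of" at least 4 points.

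Protocol 6.1.6 compares NIHSS at "three time points: pre-operation, 24 ± 12 h postoperatively and 7 ± 2 d postoperatively". Under protocol 6.2.1.3, the first scheduled postoperative NIHSS and the postoperative CT or MR both belong to Visit 3, at 24 ± 12 h. SAP section 4 states "Missing safety data were not imputed". Table 33 offers No, Yes and a total with the number missing.

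**The concern.** sICH is the only listed safety endpoint specific to bleeding, and comparing it between arms is a stated aim (protocol 3.2, SAP 1.3). A haemorrhage that kills quickly is the most severe form of the event. Yet it can fail the written definition because the patient did not live to be scored. Such a patient stays in the denominator of the formulas but cannot enter the numerator. The error runs one way: it can only lower the rate. At stake is the accuracy of one safety rate, which would reasonably inform the judgement in protocol 8.2 that there are no clinically unacceptable safety issues related to the device.

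**Working it through.** **Step 1: trace a treated patient through the written rule.**

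| Patient | Bleed on CT/MR within 24 h | NIHSS rise of at least 4 recorded | Table 33 |
|---|---|---|---|
| Bleeds, is scanned and scored (scheduled or not, comatose or not) | yes | yes | Yes |
| Bleeds, is scanned, dies with no postoperative NIHSS | yes | cannot be met | No or Missing |
| Dies without a postoperative scan | not shown | with or without a score | not Yes, because the imaging condition fails |

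The second row is the gap. Nothing elsewhere closes it:

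- The NIHSS appendix (protocol Appendix 5) assigns no score to death, whereas the mRS (Appendix 4) gives death a 6.
- The Visit 3 window runs from 24 − 12 = 12 h to 24 + 12 = 36 h, so no score is scheduled before 12 h.
- SAP section 4 rules out imputation.
- The plan does not say whether the patient is then a No or a Missing.

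**Step 2: reproduce the plan's arm size, used here only as a denominator.** Inputs from protocol 7.2.1: 89% in both arms, margin 12.5%, one-sided alpha 0.025, power 80%.

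n = (1.960 + 0.842)² × 2 × 0.89 × 0.11 / 0.125² = 7.85 × 0.1958 / 0.015625 ≈ 98.4, so 99 per arm. With 10% dropout, 99 / 0.9 = 110 per arm, 220 in total. The plan's figures reproduce.

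**Step 3: effect per affected patient.** 1/110 = 0.91 points; 1/99 = 1.01 points. The documents give no sICH rate and no early-death rate, so the count is an assumption. One to three such patients in one arm would remove 0.9 to 2.7 points at 110, or 1.0 to 3.0 points at 99. Zero is also possible.

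**Step 4: an assumed example.** Take 6 true sICH among 110 in one arm and 3 among 110 (2.73%) in the other, with a two-sided Fisher exact test.

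| Lost in first arm | Rate, all treated | Rate if Missing leaves the denominator | Fisher p (all treated) v 3/110 |
|---|---|---|---|
| 0 | 6/110 = 5.45% | 5.45% | 0.499 |
| 1 | 5/110 = 4.55% | 5/109 = 4.59% | 0.721 |
| 2 | 4/110 = 3.64% | 4/108 = 3.70% | 1.000 |

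The choice between No and Missing changes the rate by less than 0.1 point. In this example the finding of no significant difference is the same throughout.

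**The case against.** The strongest objection is that the case is very narrow. Appendix 5 scores unresponsive patients: item 1a has a top value for them, and items 8 and 9 assign fixed values in coma. Protocol 6.1.7 does not confine the NIHSS to the scheduled visit. A patient who deteriorates from a bleed can thus be scored up to the point of death, and an unscheduled score or scan within 24 h counts. That stands. It limits the gap to patients scanned with a bleed and never scored after the procedure, and there may be none.

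Several stronger readings are tempting, and the documents do not support them.

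- *Every early fatal bleed is lost through the NIHSS rule.* This merges two failures. A death without a scan fails the separate CT/MR condition. A death clause would not change that, and nothing shows that such a death was haemorrhagic.
- *Unscanned early deaths should be counted as sICH in a worst-case row.* That would conflict with the no-imputation rule in SAP section 4 and could add non-haemorrhagic deaths to a low-count endpoint.
- *Table 33 contradicts the coded event tables.* Tables 37 and 38 have no 24 h window and no NIHSS condition, so they differ from Table 33 partly by design.
- *The deaths disappear from the report.* They do not. Table 34 shows all-cause mortality by arm, Table 36 has a row for "Serious adverse events resulting in death", and Tables 35, 37 and 38 cover the adverse events.
- *The trial's result is at risk.* The only numerical pass criterion in protocol 8.2 concerns recanalization.

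**Conclusion.** The point holds as a minor gap in the definition. By the written rules, a treated patient with intracranial haemorrhage on CT or MR within 24 h who dies before a postoperative NIHSS is recorded cannot count as sICH. The undercount is about 0.9 to 1.0 percentage points of that arm's rate per patient, always downwards. This follows from the text; the number of such patients is unknown and may be zero. The 6 v 3 example rests on assumed counts and shows scale only. The primary endpoint, the sample size and every numerical decision rule are untouched. The only link to the pass decision is the qualitative safety judgement in protocol 8.2, which can already see every death and serious adverse event.

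**What to change.** Use one wording for deterioration in all four places (protocol 6.1.7.1, the protocol 13.3 note, SAP 2.2 item 1 and the SAP Table 33 note): *NIHSS increase of at least 4 points from preoperative, or death before a postoperative NIHSS was recorded (up to the end of the Visit 3 window, 36 h).*

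- Keep haemorrhage on CT/MR within 24 h as a condition of the endpoint, so that non-haemorrhagic deaths do not enter the rate.
- Keep all treated subjects in the denominator, as the formulas already state.
- Set the limit on death at 36 h, not 24 h. Otherwise a patient scanned with a bleed at 20 h who dies unscored at 28 h is still missed.
- Amend protocol 13.3 as well, so that the trial does not carry two sICH definitions.
- Do not count unscanned deaths as sICH. At most, footnote their number by arm under Table 33.

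The cost is one clause in four places, with ethics approval for the protocol text (protocol 12.1). The clause needs no new procedure, but the sponsor should confirm that clock times of death and end of operation are recorded, because protocol 13.1.3 does not say that event times are captured in hours. The reported sICH rate may rise slightly.

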6.7.2. All-cause mortality within 90 days postoperatively

Table34 Study All-cause mortality within 90 days

Item	Indicator	Experimental Group	Control Group	Total
All-cause mortality within 90 days post-surgery	No n(%)			
	Yes n(%)			
	Total (Missing)			
	Statistic			
	P-value			

6.7.3. Adverse Events

Table35 Summary of Adverse Events

Item	Experimental Group (n=)		Control Group (n=)		Total (n=)	
	Number of Occurrence	Incidence Rate (%)	Number of Occurrence	Incidence Rate (%)	Number of Occurrence	Incidence Rate (%)
Adverse Event						
Mild adverse events						
Moderate adverse events						
Severe adverse events						
Adverse events related to the investigational device						
Adverse events leading to subject withdrawal from the trial						
Adverse events resulting in death						

Note: Definition of trial device-related adverse events: Adverse events classified as "definitely related," "probably related," "possibly related," or "unclassifiable" to the trial device.

Table36 Summary of Serious Adverse Events

Item	Treatment Group (n=)			Control group (n=)			Total (n=)		
	Occurrence	Number of Subjects	Incidence Rate (%)	Occurrence	Number of Cases	Incidence Rate (%)	Number of cases	Incidence Rate (%)	P value
Serious Adverse Events related to the investigational device									
Serious adverse events resulting in death									

Note: Definition of serious adverse events related to the investigational device: Serious adverse events determined to be "definitely related," "probably related," "possibly related," or "unclassifiable" to the investigational device.

Table37 Event Coding

Item	Experimental Group (n=)			Control Group (n=)			Total (n=)		
	Occurrence	Number of Subjects	Incidence Rate (%)	Occurrence	Number of Cases	Incidence Rate (%)	Number of cases	Incidence Rate (%)	P value
Adverse Event									
SOC1									
PT1									
PT2									
.....									
SOC2									
.....									

Table38 Serious Adverse Event Codes

Item	Experimental Group (n=)			Control Group (n=)			Total (n=)		
	Occurrence	Number of Subjects	Incidence Rate (%)	Occurrence	Number of Cases	Incidence Rate (%)	Number of cases	Incidence Rate (%)	P value
Serious Adverse Events									
SOC1									
PT1									
PT2									

	Experimental Group (n=)	Control Group (n=)	Total (n=)	
Item	Number of Occurrence Subjects	Incidence Rate (%)	Number of Cases	Incidence Rate (%)
.....				
SOC2				
.....				

6.7.4. Cross-tabulation of Laboratory Findings Before and After Treatment

Table39 Blood Count Red Blood Cells

		24±12 hours postoperatively or 7±2 days postoperatively				
		Abnormal but not clinically significant		Abnormal but clinically significant		
Group	Screening period (-1 to 0 days)	Normal		Not Tested	Missing	Total
Experimental group	Normal					
	Abnormal but not clinically significant					
	Abnormal but clinically significant					
	Not detected					
	Missing					
Total						
Control group	Normal					
	Abnormal but not clinically significant					
	Abnormal but clinically significant					
	Not tested					
	Missing					
Total						

Table40 Complete blood count Hemoglobin

		24±12 hours post-op or 7±2 days post-op				
		Abnormal but not clinically significant		Abnormal but clinically significant		
Group	Screening Period (-1 to 0 days)	Normal		Not Tested	Missing	Total
Experimental group	Normal					
	Abnormal but not clinically significant					

Group	Screening Period (-1 to 0 days)	24±12 hours post-op or 7±2 days post-op			Missing Total
		Normal	Abnormal but clinically significant	Abnormal but clinically significant	
Control group	Abnormal but clinically significant				
	Not detected				
	Missing				
	Total				
	Normal				
	Abnormal but not clinically significant				
	Abnormal but clinically significant				
	Not tested				
	Missing				
	Total				

Table41 Complete Blood Count White Blood Cell Count

Group	Screening Period (-1 to 0 days)	24±12 hours post-op or 7±2 days post-op			Missing Total
		Normal	Abnormal but clinically significant	Abnormal but clinically significant	
Experimental group	Normal				
	Abnormal but not clinically significant				
	Abnormal but clinically significant				
	Not detected				
	Missing				
	Total				
Control group	Normal				
	Abnormal but not clinically significant				
	Abnormal but clinically significant				
	Not tested				
	Missing				
	Total				

Table42 Complete blood count Platelet count

Group	Screening Period (-1 to 0 days)	24±12 hours post-op or 7±2 days post-op			Missing	Total
		Normal	Abnormal but clinically significant	Abnormal but not clinically significant		
Experimental group	Normal					
	Abnormal but not clinically significant					
	Abnormal but clinically significant					
	Not detected					
	Missing					
Control group	Total					
	Normal					
	Abnormal but not clinically significant					
	Abnormal but clinically significant					
	Not tested					
	Missing					
	Total					

Table43 Blood Biochemistry Urea Nitrogen

Group	Screening Period (-1 to 0 days)	24±12 hours post-op or 7±2 days post-op			Missing	Total
		Normal	Abnormal but clinically significant	Abnormal but not clinically significant		
Experimental group	Normal					
	Abnormal but not clinically significant					
	Abnormal but clinically significant					
	Not detected					
	Missing					
Control group	Total					
	Normal					
	Abnormal but not clinically significant					
	Abnormal but clinically significant					
	Not tested					
	Missing					

Group	Screening Period (-1 to 0 days)	24±12 hours post-op or 7±2 days post-op			Missing Total
		Normal	Abnormal but not clinically significant	Abnormal but clinically significant	
	Total				

Table44 Blood Biochemistry Urea

Group	Screening Period (-1 to 0 days)	24±12 hours post-op or 7±2 days post-op			Missing Total
		Normal	Abnormal but not clinically significant	Abnormal but clinically significant	
Experimental group	Normal				
	Abnormal but not clinically significant				
	Abnormal but clinically significant				
	Not detected				
	Missing				
Control group	Total				
	Normal				
	Abnormal but not clinically significant				
	Abnormal but clinically significant				
	Not tested				
	Missing				
	Total				

Table45 Blood Biochemistry Blood Creatinine

Group	Screening Period (-1 to 0 days)	24±12 hours post-op or 7±2 days post-op			Missing Total
		Normal	Abnormal but not clinically significant	Abnormal but clinically significant	
Experimental group	Normal				
	Abnormal but not clinically significant				
	Abnormal but clinically significant				
	Not detected				
	Missing				
	Total				

Group	Screening Period (-1 to 0 days)	24±12 hours post-op or 7±2 days post-op			Missing Total
		Normal	Abnormal but not clinically significant	Abnormal but clinically significant	
Control group	Normal				
	Abnormal but not clinically significant				
	Abnormal but clinically significant				
	No findings				
	Absent				
	Total				

Table46 Blood Biochemistry Random Blood Glucose

Group	Screening period (-1 to 0 days)	24±12 hours post-op or 7±2 days post-op			Missing Total
		Normal	Abnormal but not clinically significant	Abnormal but clinically significant	
Experimental group	Normal				
	Abnormal but not clinically significant				
	Abnormal but clinically significant				
	Not detected				
	Missing				
	Total				
Control group	Normal				
	Abnormal but not clinically significant				
	Abnormal but clinically significant				
	Not tested				
	Missing				
	Total				

Table47 Coagulation Function Prothrombin Time

Group	Screening Period (-1 to 0 days)	24±12 hours postoperatively or 7±2 days postoperatively			Missing Total
		Normal	Abnormal but not clinically significant	Abnormal but clinically significant	
	Normal				

		24±12 hours postoperatively or 7±2 days postoperatively			
		Abnormal but not clinically significant		Abnormal but clinically significant	Not Tested
Group	Screening Period (-1 to 0 days)	Normal			Missing Total
Experimental group	Abnormal but not clinically significant				
	Abnormal but clinically significant				
	Not detected				
	Missing				
	Total				
Control group	Normal				
	Abnormal but not clinically significant				
	Abnormal but clinically significant				
	Not tested				
	Missing				
	Total				

Table48 Coagulation Function Partial Thromboelastography Time

		24±12 hours postoperatively or 7±2 days postoperatively			
		Abnormal but not clinically significant		Abnormal but clinically significant	Not Tested
Group	Screening period (-1 to 0 days)	Normal			Missing Total
Experimental group	Normal				
	Abnormal but not clinically significant				
	Abnormal but clinically significant				
	Not detected				
	Missing				
Control group	Total				
	Normal				
	Abnormal but not clinically significant				
	Abnormal but clinically significant				
	Not tested				
	Missing				
	Total				

Table49 International Normalized Ratio (INR)

Group	24±12 hours post-op or 7±2 days post-op				Missing	Total
	Screening Period (-1 to 0 days)	Normal	Abnormal but clinically significant	Abnormal but not clinically significant		
Experimental group	Normal					
	Abnormal but not clinically significant					
	Abnormal but clinically significant					
	Not detected					
	Missing					
Control group	Total					
	Normal					
	Abnormal but not clinically significant					
	Abnormal but clinically significant					
	Not tested					
	Missing					
	Total					

